Study Drugs	
Neoadjuvant pembrolizumab will be administered at a fixed dose of 200 mg (IV) for 1 cycle plus 200 mg vactosertib (PO QD, 5 days per week x 2 weeks).
 
Adjuvant pembrolizumab (400 mg IV) + vactosertib (200 mg PO QD Cycle 1, 5 days per week, Cycles 2 and beyond 200 mg BID, 5 days per week) will be administered for up to eight 6-week cycles.

Phase 2, Pembrolizumab, Vactosertib

Safety Assessments	Safety assessments will include adverse events, clinical laboratory evaluations, and vital signs.
Efficacy Assessments	Objective response rate, pathologic response rate, R0 resection rate, and 1-year and 2-year RFS.
Unique Aspects of this Study	This is the first study to evaluate the safety and efficacy of pembrolizumab plus vactosertib following FOLFOX chemotherapy in patients with metastatic CRC undergoing liver resection with curative intent. Biopsy of a liver metastasis prior to administering pembrolizumab plus vactosertib and resection of the liver metastases following 1 cycle of pembrolizumab plus vactosertib will enable extensive scientific correlatives.

Study Schema

The above timeline is approximate with further guidelines below:

- A screening computed tomography (CT) chest/abdomen/pelvis with intravenous (IV) contrast must be performed and reviewed to confirm candidacy for hepatic resection prior to study entry.
- If chemotherapy is a direct lead-in to study enrollment, then liver resection surgery should be performed within 4-6 weeks of the final chemotherapy administration. During this 4-6 week window, 1 cycle of pembrolizumab plus vactosertib will be administered approximately 2 weeks (minimum 1 week) after the last dose of chemotherapy, and surgery will occur approximately 2 weeks (minimum 1 week) after C1D1.
- Labs, including liver function testing will be performed after C1D1, as close to surgery as possible.

Phase 2, Pembrolizumab, Vactosertib

- In the event that the surgery is canceled, and the first liver biopsy yielded adequate tumor material, a second liver biopsy will be requested (same lesion as the first biopsy preferred).
- Participants will be followed for up to 2 years after surgery or will be offered optional adjuvant treatment (described below).

Optional Adjuvant Treatment

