As in the Nordlinger study, we typically give 6 cycles of FOLFOX to patients with synchronous metastases who are candidates for liver resection [6]. Practice patterns vary greatly for patients with metachronous metastatic disease, based on the specific circumstances, hence flexibly was built into this protocol for feasibility. When applicable, it is then standard to wait 4 to 8 weeks from the time of last FOLFOX administration until surgery. This waiting period represents a window of opportunity to intervene.

Additionally, only about 30% of patients with hepatic metastases treated with curative intent actually achieve cure [2, 27]. Most recurrences occur within 2 years of surgery, so 2-year relapse-free survival (RFS) is a common intervention endpoint [28, 29]. Importantly, despite the high recurrence rate, observation is recommended after surgery for resectable metastases in patients who have received prior oxaliplatin-based therapy because no standard chemotherapy has been proven to improve RFS [30]. Introduction of experimental adjuvant therapy after metastasectomy offers another opportunity for intervention, with a goal to clear any remaining micrometastatic disease.

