5.1.3 Other Modality(ies) or Procedures

Patients are expected to undergo standard of care surgical resection of liver metastases within 4-6 weeks of the final chemotherapy administration (if applicable) and approximately 2 weeks (minimum 1 week) after their neoadjuvant dose of pembrolizumab-base treatment. Standard of care operative plan is at the discretion of the treating surgeon.

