5.1.4 Dose Limiting Toxicity

As the toxicities of pembrolizumab are well-established and not necessarily dose-dependent, this study will not use formal dose-limiting toxicity definitions according to NCI CTCAE grading criteria. However, to avoid compromising patient safety in this potentially curative setting, early stopping rules will be followed such that the study will be stopped, and this approach re-evaluated, if 2 or more of the first 6 patients experience any 1 of the following:

- A delay in planned surgery beyond the 8-week window after final chemotherapy treatment due to any grade toxicity attributable to study treatment. Delays in surgery due to other reasons (scheduling, available operating room time, patient preference) will not count.
- Grade IV and V surgical complications according to Clavien-Dindo classification (Appendix 4).

Note: Surgical complications associated with liver metastasectomy are very common, and we recognize that it may be difficult to attribute any such complications to preoperative administration of pembrolizumab-based treatment. Therefore, the occurrence of such events may not necessarily require stopping the study early, but will be discussed amongst members of the JSC, and Merck with particular attention paid to specific complications such as liver failure, severe colitis, etc.

Moreover, enrollment will be paused for 4 weeks after the sixth patient undergoes surgery (or receives their dose of pembrolizumab-based treatment if unable to undergo surgery). During this interval the study investigators will meet with the participating surgeons and Merck to review the first 6 cases. A recommendation will be made regarding whether or not to enroll additional patients and if any changes are needed to optimize safety or feasibility.

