6.2 Trial Flow Chart

Table 10 Main Trial Flow Chart

Trial Period: Treatment Cycle/Visit:	Screening	Preoperative Treatment	Pre-Surgery	Surgery	Post-Surgery Safety F/U	Follow Up Phase ^{a,m}
		C1D1				
Scheduling Window:	-28d to -1d	≥7d post-last chemotherapy	+7-14d post-C1D1	+7-14d post-C1D1, 28-42d post-last chemo	14d ±7d post-op	Q90D ±14d post-op for up to 2y
Directed Medical History	X					
Main Trial Study Informed Consent	X ^b					
Future Biomedical Research consent (optional)	X ^b					
Inclusion/Exclusion Criteria	X					
Demographics and Full Medical History, including MMR/MSI status	X				X ^c	
Prior and Concomitant Medication Review	X ^d	X	X	X	X	X ^k
History of Prior Treatments and residual toxicity to prior treatment	X					
Trial Treatment Administration ^j		X				
Dispense vactosertib supply		X				

Trial Period: Treatment Cycle/Visit:	Screening	Preoperative Treatment	Pre-Surgery	Surgery	Post-Surgery Safety F/U	Follow Up Phase ^{a,m}
		C1D1				
Scheduling Window:	-28d to -1d	≥7d post-last chemotherapy	+7-14d post-C1D1	+7-14d post-C1D1, 28-42d post-last chemo	14d ±7d post-op	Q90D ±14d post-op for up to 2y
Post-study anticancer therapy status						X ^k
Survival Status						X
Review Adverse Events		X	X		X	X ^k
Complete Physical Examination	X					
Directed Physical Examination		X	X		X	
Vital Signs and Weight	X	X	X		X	
ECOG Performance Status	X ⁱ	X	X		X	
Pregnancy Test – Urine or Serum	X					
PT/INR and aPTT	X ⁿ		X			
Hematology, CBC with Differential and platelet count	X ⁿ	X	X		X	X ^a
Comprehensive Serum Chemistry Panel (see Table 12)	X ⁿ	X	X		X	X ^a
Urinalysis	X	X	X		X	X ^a

Trial Period: Treatment Cycle/Visit:	Screening	Preoperative Treatment	Pre-Surgery	Surgery	Post-Surgery Safety F/U	Follow Up Phase ^{a,m}
		C1D1				
Scheduling Window:	-28d to -1d	≥7d post-last chemotherapy	+7-14d post-C1D1, 28-42d post-last chemo	+7-14d post-C1D1, 28-42d post-last chemo	14d ±7d post-op	Q90D ±14d post-op for up to 2y
T3 (free and total), FT4 and TSH	X	X	X		X	X ^a
Tumor Marker: CEA p.	X	X	X		X	
Hep B surf Ag, Hep B sur Ab, Hep B core Ab, Hep C RNA	X					
Echocardiogram (ECHO)	X					
Electrocardiogram (ECG)		X ⁱ				
Disease Status Assessment/ Measurable disease	X		X			X
Tumor Imaging ^h	X ^g					X
Archival Tissue Collection		X ^o				
Biopsy of Liver Metastasis	X				X ^e	
Hepatic metastasectomy				X		
Correlative Studies: Blood Collection		X	X		X	X ^k
Correlative Studies: Stool	X		X		(X)	

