8.3 Interim Analyses and Stopping Rules

The trial will be stopped early if 2 of the first 6 patients fail to undergo liver resection surgery within 6 weeks of their final chemotherapy treatment (if applicable) due to AEs attributed to pembrolizumab-based treatment, or experience Grade IV-V surgical complications according to Clavien-Dindo classification attributed to pembrolizumab -base treatment (Appendix 4).

Of particular significance to this study, enrolling patients being treated with curative intent, are perioperative complications attributed to pembrolizumab-based treatment. These may include delaying surgery due to pre-operative AEs and complications during or after surgery attributed to pembrolizumab-based treatment. Early stopping rules have been defined to mitigate risk of perioperative complications. The study will be stopped and the approach will be re-evaluated if 2 or more of the first 6 patients experience any one of the following:

- A delay in planned surgery beyond the 6-week window from final chemotherapy (if applicable), due to any grade toxicity attributable to study treatment. Delays in surgery due to other reasons (scheduling, available O.R time, patient preference) will not count.
- Grade IV and V surgical complications according to Clavien-Dindo classification (Appendix 4). *Note:* Surgical complications associated with liver metastectomy are very common, and we recognize that it may be difficult to attribute any such complications to preoperative administration of pembrolizumab. Therefore, the occurrence of such events may not necessarily require stopping the study early, but will be discussed amongst members of the JSC, with particular attention paid to specific complications such as liver failure, severe colitis, etc.

Enrollment will be paused for 4 weeks after the sixth patient undergoes surgery (or receives their last dose of pembrolizumab if unable to undergo surgery). During this interval the study investigators will meet with the participating surgeons to review the first 6 cases. A recommendation will be made regarding whether or not to enroll additional patients and if any changes are needed to optimize safety or feasibility.

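### The first-six-patients stopping rule has two limits for a toxicity delay of surgery, 6 weeks in section 8.3 and 8 weeks in section 5.1.4, and the 5.1.4 figure is the outlier

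*Combined protocol and SAP*

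**What the plan says.** Section 8.3 (Interim Analyses and Stopping Rules) stops the study if at least two of the first six patients have one of two listed events. The delay event reads: "A delay in planned surgery beyond the 6-week window from final chemotherapy (if applicable), due to any grade toxicity attributable to study treatment". The opening sentence of 8.3 also uses 6 weeks.

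Section 5.1.4 (Dose Limiting Toxicity) states the rule again. Its delay event reads: "A delay in planned surgery beyond the 8-week window after final chemotherapy treatment due to any grade toxicity attributable to study treatment".

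Other places bear on which limit was meant:

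- Section 8.1, under the safety endpoint, refers the reader to section 8.3 for the early stopping rules.
- Table 10 in section 6.2 schedules surgery at "7-14d post-C1D1, 28-42d post-last chemo".
- Sections 5.1.3 and 6.1.4 expect surgery 4 to 6 weeks after the last chemotherapy, and the feasibility criterion in 8.4.3 uses 6 weeks.
- Section 3.2 suspends accrual if two or more of the first six patients do not reach surgery in the 4 to 6 week window, or have surgical complications attributed to treatment.
- Section 1.3, as background on usual practice, says "it is then standard to wait 4 to 8 weeks from the time of last FOLFOX administration until surgery".

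**The concern.** This is the protocol's only numerical early stopping boundary, and it protects patients who are being treated with curative intent. A boundary of this kind should give the same answer wherever it is read. Here a patient whose surgery slips into week 7 or 8 because of the study drugs is an event in one section and not in the other. A team working from the treatment plan in section 5 could leave uncounted a patient whom the statistical section counts.

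The later safeguards do not settle which limit applies. The enrollment pause begins only after the sixth patient's surgery (or dosing, if there is no surgery), while two qualifying delays could occur before that.

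**Working it through.** The documents state no stopping probability or delay rate for this rule, so there is no figure to reproduce. The check is a comparison of the text, with simple day counts.

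**Step 1. Are these one rule or two?**

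| Element | Section 8.3 | Section 5.1.4 |
|---|---|---|
| Count | 2 or more of first 6 | 2 or more of first 6 |
| Cause of delay | toxicity of any grade due to study treatment | same |
| Delays not counted | scheduling, operating-room time, patient preference | same |
| Other listed event | Clavien-Dindo Grade IV-V | same |
| Consequence | study stopped, approach re-evaluated | same |
| Delay limit | beyond 6 weeks | beyond 8 weeks |
| If-applicable qualifier | present | absent |

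Apart from the limit and the qualifier, the delay rule is the same. Nothing presents the two as a warning tier and a stopping tier.

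**Step 2. Size of the gap.** The limits are 6 × 7 = 42 days and 8 × 7 = 56 days, a difference of 56 − 42 = 14 days. Surgery on days 43 to 56 after the last chemotherapy, late because of study-drug toxicity, counts under 8.3 only.

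**Step 3. How large a slip falls in the gap?** The Study Schema puts C1D1 about 2 weeks after chemotherapy and says "surgery will occur approximately 2 weeks (minimum 1 week) after C1D1". Planned surgery is then near day 14 + 14 = 28.

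- Planned at day 28: from 43 − 28 = 15 to 56 − 28 = 28 days of slip.
- Planned at day 42, the end of the Table 10 window: from 43 − 42 = 1 to 56 − 42 = 14 days of slip.

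**Step 4. Which limit is the outlier?**

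| Limit | Where it appears |
|---|---|
| 6 weeks | 8.3 (opening sentence and listed event), 3.2, 5.1.3, 6.1.4, Table 10 (28 to 42 days), 8.4.3 |
| 8 weeks | 5.1.4 (stopping limit), 1.3 (background on usual practice) |

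The cross-reference for the stopping rules, in section 8.1, also points to 8.3. It is a pointer and not a formal precedence clause, but it agrees with the rest of the protocol.

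**The case against.** The best defence is that the two sections do not contradict each other in logic. Each gives a condition for stopping, and 5.1.4 nowhere says that the study continues when delays stay within 8 weeks. A team that obeys both sections stops at the earlier limit, as the pointer in 8.1 supports. This stands. A reader might infer that the sections give opposite instructions or that the trial has no usable boundary; the documents do not support that. What remains is a wrong or stale number in one statement of a safety rule.

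It can also be said that 8 weeks was a deliberate margin beyond the planned window, in line with the practice described in 1.3. That is possible, but 5.1.4 gives no such reason and 8.3 uses 6 weeks twice.

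Several safeguards limit the consequence. Section 3.2 suspends accrual on the 6-week window whatever the cause. Enrollment pauses for 4 weeks after the sixth patient. Section 6.8 allows termination for adverse reactions without a patient count. The Site Committee and the Data and Safety Monitoring Committee review safety throughout. Section 6.1.4 has surgery go ahead as planned when vactosertib is held, unless there are safety concerns about the surgery. All of this stands and keeps the point modest.

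Three wider readings are tempting and should not be drawn:

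- **Section 3.2 as a third conflicting version.** Its consequence is suspension of accrual, not stopping. A broad suspension trigger beside a narrower stopping rule is an ordinary two-tier arrangement.
- **Grade IV-V complications counted inconsistently.** The listed event carries no attribution condition, but the text that introduces the list in 8.3 speaks of "complications during or after surgery attributed to pembrolizumab-based treatment", and the Note refers such cases to the JSC. These can be read as one procedure.
- **No cover for patients without lead-in chemotherapy.** The delay clock has no start date for them, but the complication limb still applies, and so does the timely-surgery wording in 3.2.

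**Conclusion.** The inconsistency is real and is in the current text. Sections 5.1.4 and 8.3 state the same stopping rule with limits 14 days apart, and two toxicity-delayed surgeries in weeks 7 to 8 meet one and not the other. The 5.1.4 figure is the one out of line. The mismatch concerns patients whose chemotherapy led directly into the study, since both limits run from the final chemotherapy.

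This conclusion rests on the wording alone and needs no assumed rate. A reader might want a probability that the two versions disagree. Any such figure would come from assumed delay rates, and the documents give none, so none is claimed. The primary TIL analysis is not affected. The point is worth correcting because it concerns a safety threshold and the correction is nearly free; the practical risk is modest.

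**What to change.** In section 5.1.4, change the delay limit from 8 weeks to 6 weeks, add the if-applicable qualifier that 8.3 carries, and state that section 8.3 is the governing rule.

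Leave two things alone. The suspension trigger in section 3.2 should stay: replacing it with a cross-reference to 8.3 would remove its all-cause surgery trigger and its trigger for attributed complications of any grade. The JSC procedure for judging Grade IV-V complications should also stay. Suspending before attribution is judged would be a trade-off against the sponsor's own Note, and this inconsistency does not require it. Nor should the 7 to 14 day post-C1D1 window become a stopping clock for patients without lead-in chemotherapy, because that would leave no slack: a toxicity-delayed operation on day 15 would count.

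The cost is a short protocol amendment with the usual approvals, and no new data or procedures. The downside is that the rule as written in 5.1.4 could trigger slightly more often than it would at 8 weeks, though no more often than 8.3 already requires for toxicity delays.

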8.4 Analyses Plans

8.4.1 Analysis Population

The analysis population for the primary outcome will be all patients with pre- and post-pembrolizumab-based neoadjuvant treatment tumor specimens that are evaluable for TILs.

The All Patients as Treated (APaT) population will be used for the analysis of the secondary safety/toxicity outcomes and the clinical efficacy endpoint, ORR. The APaT population consists of all patients who received at least one dose of pembrolizumab and/or vactosertib and at least one laboratory or vital sign measurement. To assess change from baseline, a baseline measurement is also required.

Patients who undergo surgical resection of liver metastases will be evaluable for the secondary clinical efficacy endpoints: pathologic response rate, R0 resection rate and RFS at 2-years.

Safety analyses will be performed for all patients having received at least one dose of pembrolizumab and/or vactosertib. The study will use the NCI CTCAE v5.0.

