2.3 Secondary Objectives and Endpoints

Secondary Objectives	Endpoints	Time Frame
1. To establish the safety/toxicity profile of pembrolizumab-based treatment in the perioperative setting for patients with CRC with resectable hepatic metastases.	
 Proportion of participants with Adverse Events, as graded by NCI CTCAE version 5.0 Proportion of participants with events of clinical interest (ECIs) Rates of perioperative complications 	From initiation of study treatment until 1 year post last dose of pembrolizumab.
2. To explore the efficacy of pembrolizumab plus vactosertib in patients with CRC with resectable hepatic metastases.	
 R0 resection rate Pathologic response in resected tumor Objective response rate 2-year relapse-free survival (RFS) 	From baseline to surgery. From surgery to up to 2 years post-surgery.

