6.1.6 Optional Adjuvant Treatment

6.1.6.1 Pre-treatment

Participants interested in participating in the optional adjuvant treatment cohort (pembrolizumab + vactosertib) will complete the pre-treatment procedures 2 weeks (± 7 days) after surgery.

Study procedures and assessments:

- Informed consent for adjuvant treatment
- Review of eligibility (per the investigator's discretion). The rationale for enrolling (or not enrolling) participants in adjuvant therapy will be recorded, along with any supporting test results (e.g., circulating tumor DNA analysis).
- Concomitant medications
- Evaluation of AEs
- Directed physical examination
- Vital sign measurements and weight
- ECOG Performance status
- Serum or urine pregnancy test within 72 hours prior to the start of adjuvant treatment
- PT/INR and aPTT
- Hematology (other than CDC with diff), CBC with differential and platelet count

- Comprehensive serum chemistry (see Table 12)
- Urinalysis
- T3 (free and total), FT4 and TSH

Participants who are ineligible for the adjuvant treatment cohort will be followed every 90 days (Q90D; \pm 14 days) for up to 2 years post-surgery per Table 10 and section 6.1.7.

6.1.6.2 Cycle 1 through Cycle 8

Eligible participants will receive adjuvant treatment 6 weeks (\pm 2 weeks) after hepatic metastasectomy. Participants will receive adjuvant pembrolizumab + vactosertib for up to eight, 6-week cycles (approximately 1 year) or until disease recurrence is radiographically documented, unacceptable AE(s), intercurrent illness that prevents further administration of treatment, investigator's decision to discontinue the patient, administrative reasons requiring cessation of treatment, or withdrawal of consent, whichever occurs first.

Perform the following procedures and assessments on day 1 of each cycle unless specified otherwise:

- Concomitant medications
- Evaluation of AEs
- Directed physical examination
- Vital sign measurements and weight
- ECOG Performance status
- Hematology (other than CBC with diff), CBC with differential and platelet count*
- Comprehensive serum chemistry (see Table 12)*
- Urinalysis*
- T3 (free and total), FT4 and TSH*
- ECHO - perform at cycle 2 only
- Tumor Marker: CEA
- Tumor imaging with IV contrast to monitor disease status - perform every 12 weeks (i.e., day 1 of every other cycle)
- Correlative studies blood collection - perform every 12 weeks (i.e., day 1 of every other cycle)
- Pembrolizumab administration (see section 5.1)

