7.3.5 Events of Clinical Interest

Selected non-serious and SAE are also known as ECIs.

Events of clinical interest that must be reported to Merck include:

1. An overdose of Merck's product, as defined in Section 7.3.4, that is not associated with clinical symptoms or abnormal laboratory results.
2. An elevated AST or ALT lab value that is greater than $5 \times$ ULN and an elevated total bilirubin lab value that is greater than or equal to $2 \times$ ULN and, at the same time, an ALP lab value that is less than $2 \times$ ULN, as determined by way of protocol-specified laboratory testing or unscheduled laboratory testing.*

Note: Liver function test abnormalities are expected after hepatic metastatectomy. Therefore, AST, ALT or total bilirubin elevations occurring after hepatic metastatectomy and considered by an investigator who is a qualified physician to be related to surgery (unlikely related to pembrolizumab), must be reported to the Sponsor and to Merck at the time of the first post-surgical safety follow-up visit or within 30 days of hepatic metastatectomy surgery, whichever comes first.

*Note: These criteria are based upon available regulatory guidance documents. The purpose of the criteria is to specify a threshold of abnormal hepatic tests that may require an additional evaluation for an underlying etiology.

Phase 2, Pembrolizumab, Vactosertib

Events of clinical interest that must be reported to MedPacto include:

1. Any abnormal changes in cardiac valves detected by ECHO which will be conducted at the screening, cycle 2 during adjuvant treatment, and EOT.

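### Operative complication rates are assigned to all treated patients, including those never operated on, and the 17 in the feasibility limit matches neither that set nor a defined operated set

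*Combined protocol and SAP*

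**What the plan says.** Section 8.4.1 fixes the analysis sets. For safety, "The All Patients as Treated (APaT) population will be used for the analysis of the secondary safety/toxicity outcomes". That set "consists of all patients who received at least one dose of pembrolizumab and/or vactosertib" and have at least one laboratory or vital sign measurement. Surgery is not a condition of membership.

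Section 2.3 places "Rates of perioperative complications" under the safety objective, next to the proportions with adverse events and with events of clinical interest (ECIs). Section 8.1 says that surgical complications will be graded by Clavien-Dindo.

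Section 8.4.1 also has a surgical set: "Patients who undergo surgical resection of liver metastases will be evaluable for the secondary clinical efficacy endpoints". The endpoints it names are pathologic response, R0 resection and 2-year relapse-free survival. Operative complications are not among them.

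Section 8.4.3 gives the only numerical criterion for complications: serious, attributable postoperative complications must not exceed 33%, which it equates with 6 of 17 patients. Section 3.2 plans 19 enrolled to obtain 17 evaluable for the primary endpoint.

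On heart valves, Section 7.3.5 lists as an ECI "Any abnormal changes in cardiac valves detected by ECHO which will be conducted at the screening, cycle 2 during adjuvant treatment, and EOT". Table 10 schedules echocardiography (ECHO) at screening only. In the adjuvant cycles the instruction is "ECHO - perform at cycle 2 only", and the End of Treatment ECHO in Section 6.1.6.3 is conditional on there being no recent one.

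**The concern.** A rate of operative complications is meant to describe the risk of surgery after this treatment. Read literally, Section 8.4.1 divides by everyone dosed. Patients whose operation is cancelled then count as free of surgical complications, although they were never exposed to surgery.

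The plan expects such patients. Section 6.1.4 provides a second biopsy when surgery is cancelled, and Section 8.3 provides for patients who cannot have surgery.

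The error runs in one direction. More cancelled operations mean a lower reported complication rate for the same experience among those operated on. That favours the hypothesis in Section 2.1 that treatment does not raise perioperative complications. It also bears on the feasibility judgement in Section 8.4.3, where a percentage limit is applied without a defined denominator.

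**Working it through.** **Inputs**
- Treated patients: 19, the planned enrolment (Section 3.2), assuming all are dosed.
- Share reaching surgery: 87.3%, which Section 1.3.1 quotes from the cited EORTC perioperative chemotherapy trial. The plan gives no projection of its own.
- Complication limit: 33%, or 6 of 17 (Section 8.4.3).

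**1. The plan's own figure**
- 6/17 = 35.3%, so the count and the percentage disagree. Six of 17 meets the limit as a count and breaks it as a percentage. 5/17 = 29.4%; 33.3% would be 6/18.
- The companion criterion has the same fault: 14/17 = 82.4%, below the stated 83%; 15/18 = 83.3%.

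**2. Which patients are the 17?**
- They are not the all-treated set, which may be up to 19.
- They are not defined as the operated patients.
- The number equals the target for paired tumour specimens, and that group can include unresected patients who had a second biopsy (Section 6.1.4).

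**3. Size of the dilution**

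Rate over treated = rate over operated × (operated / treated). Expected operated = 19 × 0.873 = 16.6, about 17.

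| Operated, of 19 | Factor | 5 events / operated | 6 events / operated | 7 events / operated |
|---|---|---|---|---|
| 19 | 1.000 | 26.3% | 31.6% | 36.8% |
| 18 | 0.947 | 27.8% | 33.3% | 38.9% |
| 17 | 0.895 | 29.4% | 35.3% | 41.2% |
| 16 | 0.842 | 31.2% | 37.5% | 43.8% |
| 14 | 0.737 | 35.7% | 42.9% | 50.0% |

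Over all 19 treated, the rates are those in the first row, whatever the number operated on.

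**4. Effect on the 33% limit**

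With 17 operated, five events pass on either denominator (26.3% and 29.4%) and seven fail on either (36.8% and 41.2%). Six is the count at which the choice decides: 31.6% over treated, 35.3% over operated. With 14 operated, five events also change sides (26.3% against 35.7%).

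**5. Valve change**

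The number entering the optional adjuvant phase is not given. If 10 of 19 have a post-treatment ECHO (an assumption), one event is 5.3% of treated patients and 10.0% of those examined. With no events, the one-sided 95% upper bound, 1 − 0.05^(1/n), is 14.6% at n = 19 and 25.9% at n = 10. Over an assumed range of 4 to 19 examined, the ratio of the two rates runs from 0.21 to 1.0.

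**The case against.** **The plan may not intend 19.** Section 8.4.3 uses 17, so an analyst might never compute 6/19. This stands in part: the two sections disagree. It does not remove the problem, because 17 is not tied to patients who had surgery.

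**Some perioperative events can occur without surgery.** Section 8.3 counts delay of surgery caused by pre-operative adverse events among perioperative complications. A reader might infer that every perioperative measure should move to operated patients. The documents do not support that. A patient who never reaches the operating room can have the delay event, and all treated patients are the right denominator for it. Only intra- and post-operative complications need the narrower set.

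**The consequence is limited.** Section 8.4.3 makes these analyses descriptive and calls the sample too small for comparison with historical data. The exact 95% intervals overlap almost wholly: 12.6% to 56.6% for 6/19 and 14.2% to 61.7% for 6/17. This stands as to precision. The feasibility limit, however, is applied to the point estimate.

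**Valve change.** A reader might infer that a cardiac-valve rate is also understated because unexamined patients cannot have the event. The documents do not support this, for two reasons. No separate valve rate is planned: valve change is one component of the ECI proportion in Section 2.3, for which all treated patients are a reasonable denominator. And a patient without a later ECHO can have a valve change that goes undetected. That is a gap in ascertainment, which a smaller denominator does not close. Examined patients would be mainly those selected for adjuvant treatment, so their rate would not describe neoadjuvant exposure alone.

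**Conclusion.** The point holds for intra- and post-operative complications. As written, Section 8.4.1 puts patients who were never operated on into their denominator, and Section 8.4.3 uses a 17 that agrees with no defined set and a percentage that does not equal its count.

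The expected dilution is modest: a factor of about 0.87 to 0.90 at the cited trial's resection share (0.873 itself, or 17/19 = 0.895 in whole patients). It is 0.737 if only 14 of 19 are operated on, and there is none if all 19 are. It can still change the feasibility conclusion, at six events in the central case. These sizes assume 19 treated patients and a share reaching surgery borrowed from another trial.

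The point does not extend to adverse events generally, the overall ECI proportion, or delay or cancellation of surgery. For valve change the documents support only a reporting caution.

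**What to change.** 1. In Section 8.4.1, name treated patients who underwent hepatic surgery as the denominator for intra- and post-operative (Clavien-Dindo) complications, and report the number of treated patients not operated on beside the rate.
2. Keep the all-treated set for adverse events, the overall ECI proportion, and treatment-related delay or cancellation of surgery.
3. In Section 8.4.3, tie the complication limit to the operated set and make its count and percentage agree. Reconcile 14 of 17 with 83% at the same time.
4. If valve change is reported separately, use patients with both a baseline and a post-treatment ECHO. Section 8.4.1 at present says only "To assess change from baseline, a baseline measurement is also required". State that the figure describes mainly adjuvant-treated patients, and that valve change was not ascertained in the others.

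The cost is a few sentences and no new procedure. The reported complication rate will be slightly less favourable and will rest on a slightly smaller number of patients.
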